- Patients undergoing surgery with intent of repair of inguinal hernia, where no hernia inguinal hernia was identified (e.g. intra-operative findings of adenopathy, femoral hernia, obturator hernia)

• Return to theatre:

- Each individual patient should only be included in the study once. Patients returning to theatre due to complications following earlier surgery can only be included if their index procedure has not already been included in the HIPPO audit.
- Patients with bilateral hernias undergoing repair with two separate procedures in two different times, should only be included for the first procedure.

6. Patient identification:

You should collect data on consecutive patients operated at your centre during the data collection period. This means that all eligible patients should be included to avoid selection bias.

Strategies to identify consecutive eligible patients could include:

- Daily review of elective and emergency theatre lists.
- Daily review of handover sheets and ward lists.
- Daily review of theatre logbooks (both elective and emergency).

7. Other variables:

Data will be collected on audit standards and confounding factors for risk-adjusted analyses. These include age, sex, body mass index, American Society of Anaesthesiologists (ASA) grade, relevant comorbidities, and smoking status. Variables including inguinal hernia features assessed pre-operatively, anaesthesia type, operative approach and technique will also be collected. Without appropriately adjusting for risk factors, it is likely that any findings would be biased and unable to be appropriately analysed on a national scale. A full list of required data fields is available in the Data Summary Document, and on the REDCap database.

8. Outcome Measures and Follow-up:

Primary outcome measure:

Compliance to audit standards described

Secondary outcome measures: (see Appendix A:)

- 30-day follow-up
- 30-day surgical site infection rates
- 30-day reoperation rates
- 30-day readmission
- 30-day Clavien-Dindo complications

Follow-up should be performed in line with current routine practice within each hospital settings. No additional telephone, in-person or questionnaire-based follow-up is required. Source data may be acquired from hospital in-patient notes, clinical electronic systems, or outpatient letters.

9. Data collection processes and governance:

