Project team structure: At each centre, this study can be delivered and disseminated by teams of medical students, junior doctors and/or consultants. Each team should include at least one specialist consultant to provide additional local support for participating medical students.

Data completeness: Following data collection, only data sets with >95% data completeness will be accepted for pooled national analysis. To emphasise the importance of data completeness to collaborators, data collection periods with >5% missing data points will be excluded from the study and collaborators from those periods withdrawn from the published list of citable collaborators.

Validation: This collaborative methodology for has been widely validated across multiple datasets, both nationally in the UK and Ireland and internationally, demonstrating high levels of case ascertainment (typically greater than 90 to 95%) and data accuracy (greater than 96 to 98%).^{16,17}

13. Authorship:

In accordance with National Research Collaborative (NRC) authorship guidelines¹⁸, all research outputs from HIPPO will be listed under a single corporate authorship ("NIHR Unit on Global Surgery").

All collaborators will be listed as PubMed-citable collaborators in accordance with the roles defined below (so long as the minimum requirements for authorship are met).

- Writing Group: A group of medical students, junior doctors, consultants and external advisory board members responsible for the overall scientific content, data analysis, and preparation of research manuscripts.
- Steering Committee: A core group of medical students, junior doctors and consultants
 who have overall responsibility for protocol design, project coordination, and data
 handling.
- Statistical Analysis: A small team of dedicated statisticians who take overall responsibility for the statistical analysis plan and quality assurance of data analysis

- National Leads: A network of surgeons and anaesthetists established with previous GlobalSurg and CovidSurg studies. They are responsible for national coordination of the study, acting as a link between mini-teams / hospital leads, and the steering committee.
 Requirements for authorship on HIPPO outputs include:
 - Active engagement with dissemination of HIPPO and other NIHR Unit on Global Surgery Collaborative activities at their country.

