 - Active involvement in data collection over at least one data collection period at a centre which meets the criteria for inclusion within the HIPPO dataset (below).
 - While assistance with other teams is encouraged, collaborator status will only be assessed based on successful completion of the allocated period.
 - Collaboration with the regional / local lead to ensure that the audit results are reported back to the audit office / clinical teams.

Criteria for centre inclusion within HIPPO:

- Obtain all appropriate local approvals for conduct of the HIPPO audit.
- Successful completion of at least one data collection period at the centre (with a minimum of one eligible patient per period included). Individual data collection periods will only be included when:
 - i. >95% data completeness has been achieved.
 - ii. All data for the period has been uploaded within the specified deadlines.

Please note if these criteria are not met, then the contributing mini-team and/or the centre may be removed from the dataset and authorship list (please get in contact as soon as potential issues arise so we can support as many centres to be included as possible).

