- 8. Arrange to meet with the other members of your mini-team, including the junior doctor and, if possible, supervising consultant. If possible, it is also highly recommended to meet with the preceding mini-team at your centre:
 - They will have a lot of helpful advice regarding what worked well. In your mini-team, agree in advance who will be responsible for each stage of the project (e.g. identifying patients, collecting baseline data, completing follow-up, data entry to REDCap).
 - Talk through how you will identify patients and collect required data.
- Identify all patients fitting the inclusion criteria within your specified four-week window.
 Contact your regional lead with any questions or issues that may arise over your data collection period.
- 10. Regularly follow-up for information on complications over the 30-day post-operative period. This study is prospective, so you should not wait until the end of the post-operative period to follow-up patients (this would be retrospective). Discuss the best way to follow up patients with the hospital lead, because this might vary from centre to centre.

Be proactive in identifying post-operative adverse events, as this will prevent underestimation of true complication rates. Remember that in this audit no changes to normal patient follow-up should be made.

Strategies for identifying complications in the follow-up period include:

- Regularly reviewing patient notes to identify in-hospital complications.
- Reviewing clinic notes and clinic letters, if seen in clinic by 30 days.
- Checking electronic systems and handover lists for re-admissions.

Checking for A&E re-attendances.

If case notes are reviewed shortly prior to discharge they do not be need to be requested/retrieved again for follow-up at 30-days, but do check electronic records for discharge letters, clinic letters, re-admissions.

- 11. Ensure all data has been uploaded to the REDCap system by the data collection deadline, and you have completed all fields, avoiding missing data points. If more than 5% of patients at your centre have missing data, your centre cannot be included in the HIPPO dataset and your name will be withdrawn from the author list.

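### The completeness gate does not separate operative from 30-day fields, so missing follow-up can remove primary-outcome data that were complete at surgery

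*Protocol*

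**What the plan says.** The protocol states the gate in three places.

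- **Section 12, Data completeness:** "only data sets with >95% data completeness will be accepted for pooled national analysis", and "data collection periods with >5% missing data points will be excluded from the study". The count is of data points, the unit removed is the period, and the removal is from the study as a whole.
- **Section 13, Criteria for centre inclusion:** "Individual data collection periods will only be included when" two conditions are met, the first being that ">95% data completeness has been achieved". The denominator is not given. The closing note is softer: "the contributing mini-team and/or the centre may be removed from the dataset and authorship list".
- **Appendix B, step 11:** "If more than 5% of patients at your centre have missing data, your centre cannot be included in the HIPPO dataset". Here the count is of patients and the unit removed is the centre.

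Section 8 gives the primary outcome as "Compliance to audit standards described". The Audit Standards section lists these as waiting time, mesh repair, the Shouldice technique where no mesh is used, and laparoscopic repair. Section 8 lists five 30-day items as secondary outcomes: follow-up, surgical site infection, reoperation, readmission and Clavien-Dindo complications. They are to come from routine practice and existing records: "No additional telephone, in-person or questionnaire-based follow-up is required".

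**The concern.** One pass/fail result, computed over all fields, decides whether a period or centre contributes to any endpoint. The primary outcome needs nothing after the day of surgery. The 30-day items depend on what each hospital happens to record afterwards, so that is where blanks are most likely. Followed as written, the rule lets a shortfall in secondary data delete complete primary data.

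The pooled count can also fail in the other direction. Under the data-point rule, 30-day fields are averaged with baseline and operative fields, so a period can meet 95% overall while its 30-day outcomes are well short of 95%.

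At stake are the number of records behind the compliance estimates and, possibly, which centres they describe. Follow-up is left to routine local practice, and the laparoscopic standard is itself conditional on resources and expertise. Centres lost through weak follow-up may therefore differ in compliance from those retained.

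**Working it through.** The 95% gate is a threshold, not a derived figure, so there is no calculation of the plan's to reproduce. The check is what each version does when only 30-day fields are missing.

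**Inputs from the protocol**
- Gate: more than 95% complete, or more than 5% missing data points (Sections 12 and 13); more than 5% of patients with missing data (Appendix B).
- Five listed 30-day items (Section 8).
- About 5,000 patients in more than 1,000 centres (Section 10): 5,000/1,000 = about 5 per centre on average.
- Minimum of one eligible patient per period (Section 13).

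**Assumptions**
- Fields per patient: F = 40, of which 5 are 30-day fields. The Data Summary Document is not shown, so a range is given below.
- A patient without follow-up has all 5 fields blank; everything else is complete.

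**1. Deletion of primary data, data-point rule (Section 12)**

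Missing share = (patients without follow-up × 5) / (patients × 40).

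| Patients in period | Without follow-up | Missing share | Result | Primary records lost |
|---|---|---|---|---|
| 1 | 1 | 5/40 = 12.5% | excluded | 1 |
| 10 | 3 | 15/400 = 3.75% | passes | 0 |
| 10 | 4 | 20/400 = 5.0% | boundary | – |
| 10 | 5 | 25/400 = 6.25% | excluded | 10 |

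In the boundary row the two sentences of Section 12 disagree: exactly 95.0% complete is not above 95%, and exactly 5.0% missing is not above 5%.

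**2. Deletion of primary data, patient rule (Appendix B)**

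One incomplete patient in a centre of n is a share of 1/n. At n = 19, 1/19 = 5.3% and the centre is excluded; at n = 20, 1/20 = 5.0% and it is not. Any centre with fewer than 20 patients is removed by a single incomplete record.

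For a centre of 5, the probability of at least one incomplete patient is 1 − (1 − d)^5, where d is an assumed, independent per-patient rate of incompleteness:

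| d | Probability that the centre is excluded |
|---|---|
| 2% | 10% |
| 5% | 23% |
| 10% | 41% |
| 20% | 67% |

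**3. What the data-point rule assures for the 30-day outcomes**

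Let s be the share of all fields that are 30-day fields, and m the share of patients lacking all of them. The missing share is m × s, so on the wording that requires more than 95% a period passes while m is below 0.05/s.

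| s | Period passes while m is below |
|---|---|
| 10% | 50% |
| 12.5% (F = 40) | 40% |
| 20% | 25% |
| 50% | 10% |

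For every s below 100% the limit exceeds 5%, so the gate never assures 95% completeness of the 30-day fields. This part does not hold if Appendix B governs, because there each patient with a blank 30-day field counts in full.

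**The case against.** **The sizes rest on a field list that is not shown.** This stands. Under Section 12, if 30-day fields are less than 5% of all fields, loss to follow-up alone cannot push a period over the limit. The deletion problem then disappears under that rule, but so does any protection of the 30-day outcomes.

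**Untraced patients may not be left blank.** Section 8 lists 30-day follow-up as an item of its own, so lack of follow-up could be a completed value, and record review could lead to an entry of no event. The protocol does not say. If such entries count as complete, deletion is less likely, but the gate then cannot detect lost follow-up.

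**Removal is not automatic.** Section 9 provides for missing-data requests, and Section 13 says that removal may follow and offers centres support. But Section 12 and Appendix B are worded as definite.

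**Endpoint-specific analysis sets belong in a SAP.** That is often so, but here the protocol itself fixes exclusion from the study.

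**Splitting the gate weakens the incentive for follow-up.** This is a fair cost; it can be met by keeping authorship tied to both blocks.

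Two stronger readings are tempting. A reader might infer that a period with most of its 30-day outcomes missing can still pass. That needs s below 10% (more than 50 fields, if only the five items count), which the documents do not establish, and it fails under Appendix B. A reader might also infer that the compliance estimate is shown to be biased. No passage links follow-up completeness to waiting time, mesh use or laparoscopy; selection is plausible, not demonstrated.

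**Conclusion.** The concern holds in a limited form. No version of the gate separates operative from 30-day fields, so each can discard primary data complete at surgery because secondary fields are missing. This assumes that missing 30-day fields are left blank and, for Section 12, that they exceed 5% of all fields. With 5 of 40 fields, a one-patient period without follow-up is excluded, and 5 of 10 patients without follow-up cost all 10 primary records. Under Appendix B the effect is stronger: one incomplete patient removes a centre of the anticipated average size.

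Separately, and only under the data-point rule, the gate does not deliver 95% completeness of the 30-day outcomes. The tolerated loss is just under 50%, 25% or 10% of patients when 30-day fields are 10%, 20% or 50% of the total.

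Which effect dominates depends on the field list, the coding of untraced patients and which version governs. Reconciling the three versions would not by itself cure the problem, since none of them splits the fields. The change is worth making before any period is excluded.

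**What to change.** 1. Compute completeness separately for (a) baseline, audit-standard and operative fields and (b) 30-day fields.
2. Decide inclusion in the primary compliance outcome on (a) only, and in the 30-day outcomes on (b) only. A period failing (b) stays in the primary outcome.
3. Count a patient recorded as not followed up as missing in (b), so that coding cannot hide lost follow-up.
4. Report the number of periods and patients failing each block.
5. State the same rule in Section 12, Section 13 and Appendix B: one denominator, one unit of exclusion, one strength of wording and one treatment of exactly 95%.

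The authorship sanction may stay tied to both blocks to keep the incentive for follow-up.

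The cost is a short protocol edit in three places and one extra completeness calculation. The primary and 30-day outcomes will have different denominators, and fewer periods may qualify for the 30-day outcomes.

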 - Effective and responsive communication with the steering committee, and with local collaborators throughout their time as Regional Leads.
 - Recruitment of centres.
 - Representation of NIHR Unit on Global Surgery Collaborative at regional educational and research meetings.
- Local (Hospital) Leads: A single lead point of contact for data collection at each site who has overall responsibility for site governance and coordinating handover between local collaborator teams. Local Leads should be prospectively identified by Regional Leads (although remain an optional role), and these are recommended to be the junior doctor or a senior medical student within the mini-team, and only one person can fulfil this role. A responsibility of the local (hospital lead) is to ensure that each mini-team is assigned a specialist consultant as supervisor.

Minimum requirements for authorship on HIPPO outputs include:

- Primary person responsible in obtaining local approvals for conduct of the HIPPO audit (e.g. obtaining local governance authorisation, adding the site to the HREC approval).
- Active involvement in a mini-team during a data collection period at the centre which meets the criteria for inclusion within the HIPPO dataset.
- Co-ordination of handover between all local collaborator teams at the centre, and involvement in local dissemination of HIPPO.
- Presentation of local results at their centre from the HIPPO audit (or otherwise arranges another collaborator to present on their behalf).
- Supervising Specialist Consultant: A supervising specialist consultant will be
 assigned for each mini team. The responsibilities of this role are to ensure that local
 guidelines are adhered to by all members of the mini-team and to ensure that any
 incidental findings made during the course of the data collection process are
 communicated to the treating inguinal hernia surgeon, according to local hospital
 policy.

- Local Collaborators (Data Collectors): A team of up to 5 people responsible for data
 collection per specialty group over a specific 4-week period at a particular centre. This
 should ideally be formed by a heterogeneous group with different levels of clinical
 training (e.g. medical students, trainees, consultants). Minimum requirements for
 authorship on HIPPO outputs include:
 - o Compliance with local audit approval processes and data governance policies.

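### Collection periods are admitted on completeness of the entered records, with no count of eligible patients, so omission of a poorly documented patient is rewarded and goes unmeasured

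*Protocol*

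**What the plan says.** Section 6 (Patient identification) asks for consecutive patients at the centre and gives the reason: "all eligible patients should be included to avoid selection bias". Section 9 repeats the aim and has the mini-team review theatre lists, ward lists and logbooks every day. Identified patients go on a Patient Identification Log that holds the hospital record number and the REDCap ID. The log never leaves the site and is destroyed when data collection ends (15 July 2023).

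Section 13 (Criteria for centre inclusion within HIPPO) decides which data enter the study. Besides local approvals it requires "Successful completion of at least one data collection period at the centre (with a minimum of one eligible patient per period included"). It adds two conditions on each period: ">95% data completeness has been achieved" and "All data for the period has been uploaded within the specified deadlines".

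Completeness is described in two ways. Section 12 says "data collection periods with >5% missing data points will be excluded from the study", and the collaborators concerned lose their citable status. Appendix B, step 11, says "If more than 5% of patients at your centre have missing data, your centre cannot be included in the HIPPO dataset", again with loss of authorship.

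On case ascertainment, the Validation paragraph of section 12 refers to earlier datasets collected with the same method, "demonstrating high levels of case ascertainment (typically greater than 90 to 95" per cent). It describes no measurement of ascertainment in HIPPO itself.

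**The concern.** The instruction and the test do not match. The instruction concerns all eligible patients. The test looks only at those entered, and a patient who was never entered cannot count against a team under either description of completeness. The stated penalties therefore fall on gaps in records, and none falls on missing patients.

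For a team with a poorly documented case, entering the patient carries a risk and leaving the patient out carries none that the protocol would detect. The gap may not be repairable, because section 8 limits follow-up to routine practice with no added contact.

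If such omissions happen and the omitted patients differ in compliance or in 30-day outcome, the estimates describe the better documented patients only. The study would also be unable to say how much was lost. A statistical analysis plan cannot repair this later, because the denominator would never have been collected.

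**Working it through.** The protocol states no figure to reproduce here. The 5,000 patients are a forecast without a formula. The check has three parts.

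**1. What each acceptance rule counts**

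| Rule | Place | Compares entered with eligible? |
|---|---|---|
| Local approvals | Section 13 | No |
| At least one eligible patient per period | Section 13 | No; it sets a floor |
| More than 95% data completeness | Section 13 | No |
| Period excluded if more than 5% of data points are missing | Section 12 | No; data points of entered patients |
| Centre excluded if more than 5% of patients have missing data | Appendix B, step 11 | No; entered patients |
| Upload by the deadline | Section 13 | No; it is a timing rule with no count to test against |

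**2. How easily one patient trips the completeness rule**

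Inputs from section 10: about 5,000 patients and more than 1,000 centres, so 5,000/1,000 = 5 patients per centre at most. This is an average per centre. A centre may run up to four periods, so the number per period may be lower.

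- *Data-point rule (section 12).* Assume that every patient has the same number of fields. With n patients entered, one of whom lacks a share m of the fields, the missing share is m/n. It exceeds 5% when m > 0.05 × n. For n = 5, m > 0.25.
- Example: m = 0.30 gives 0.30/5 = 6% missing, and the period fails. Without that patient, missingness is 0% and the period meets the completeness rule, with ascertainment of 4/5 = 80%.
- *Patient rule (Appendix B).* One patient with any gap gives 1/n. This is above 5% for every n below 20, since 1/20 = 5% exactly. At 5 patients it is 1/5 = 20%.

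The asymmetry arises under either description, so it does not depend on which one is meant.

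**3. What omission could do (illustration only)**

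If a share q of eligible patients is omitted, the true rate is (1 − q) × p_entered + q × p_omitted, and the error of the reported rate is q × (p_entered − p_omitted). The rates below are assumed and come from no document. The cited ascertainment of above 90 to 95% would put q typically below 5 to 10%. The row for 20% lies outside that range and corresponds to one patient in five.

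| q | Compliance 80% entered, 60% omitted | True complication rate if 5% entered, 10% omitted |
|---|---|---|
| 5% | 1 point too high | 0.95 × 5% + 0.05 × 10% = 5.25% |
| 10% | 2 points too high | 0.90 × 5% + 0.10 × 10% = 5.5% |
| 20% | 4 points too high | 0.80 × 5% + 0.20 × 10% = 6.0% |

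For scale, the simple 95% half-width at n = 5,000, ignoring clustering by centre, is 1.96 × √(0.80 × 0.20/5,000) = 1.1 points for compliance and 1.96 × √(0.05 × 0.95/5,000) = 0.6 points for complications. With these assumed rates, 5% omission stays inside the half-width for both outcomes. At 10% the compliance error exceeds its half-width and the complication error (0.5 points) does not. At 20% both do.

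**The case against.** The strongest reply is that omission would breach the protocol. Sections 6 and 9 and Appendix B, step 9, tell teams to identify every eligible patient. A specialist consultant is attached to each team, and section 13 says only that a team may be removed and invites early contact. This stands as far as it goes: the plan does not permit selective entry. But these are instructions to the team whose authorship depends on completeness, and none of them is a check.

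Three stronger readings are tempting, and the documents do not carry them.

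- A reader might infer that a period with, say, 1 of 20 eligible patients entered is accepted. Section 13 words its conditions on a period as necessary, not sufficient, and the one-patient minimum excludes empty periods without replacing consecutive inclusion. What can be said is that no stated rule would detect such a period.
- A reader might infer from the description of local collaborators in section 13 ("collection per specialty group over a specific 4-week period at a particular centre") that a team may cover one specialty and leave out, for example, the paediatric lists. That phrase describes team size. Sections 5 and 6 include adults and children and speak of consecutive patients at the centre.
- A reader might take the bias figures as estimates, or assume that emergency or out-of-hours cases are the ones lost. No document gives the contrast, the share omitted or the kind of patient.

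Two further points stand. The Data Summary Document is not at hand and may already accept an entry meaning not recorded, which would weaken the incentive. A self-reported count is also not independent verification. Ascertainment reporting and sensitivity analyses can be left to an analysis plan, but the count they need has to be collected at the sites.

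**Conclusion.** The point holds in a limited form. The protocol claims a consecutive cohort, but it admits data and grants authorship on rules that see only entered patients. Omission is therefore possible, rewarded and unmeasured. The documents do not show that it will occur, and its size cannot be derived from them.

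The one quantity that rests on the protocol's own figures is the sensitivity of the rule: at about 5 patients, a single entered patient with more than a quarter of fields blank exceeds the 5% limit. This assumes equal fields per patient and that a blank counts as missing. Earlier datasets suggest that losses are usually small. They cannot show what happened in HIPPO, and the log that could help is kept on site and destroyed. This is an inexpensive improvement that should be made. It is not a defect that invalidates the study.

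**What to change.** 1. In section 13, keep the one-patient minimum as a floor only. Add a criterion: at period close, and before the log is destroyed, each team enters in REDCap the number of eligible primary inguinal hernia repairs found in the theatre lists and logbooks, beside the number entered.
2. Report ascertainment overall. Repeat the primary compliance outcome in periods where all, or at least 95%, of eligible cases were entered. With fewer than 20 eligible cases these are the same condition, because one omission already exceeds 5%.
3. If the data fields do not already allow it, accept 'not recorded in notes' as an entry that does not count towards the exclusion threshold, and report how often it is used.

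**Cost:** one extra number per team per period, from sources the team already reviews daily, and one sensitivity analysis. No identifiers leave the site. The limitation is that the same team supplies the count and could undercount, so it provides a denominator but not independent verification.
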